8.5.2 Safety Analysis Populations

The ASaT population will be used for the analysis of safety data. At least 1 laboratory or vital sign measurement obtained subsequent to at least 1 dose of study treatment is required for inclusion in the analysis of each specific parameter. To assess change from baseline, a baseline measurement is also required.

Details on the approach to handling missing data for safety analyses are provided in Section 8.6 (Statistical Methods).

8.6 Statistical Methods

8.6.1 Statistical Methods for Efficacy Analyses

This section describes the statistical methods that address the primary and secondary objectives. Methods related to exploratory objectives will be described in the sSAP.

Data from the training set (first 100 subjects in Cohort A) will be evaluated for biomarker analysis and cut point determination. The analysis of confirmation set (150 subjects in Cohort A) will focus on verifying the response rate above the cut point is consistent with predictions made based on the training set data used to set the cut point via the interim analysis. Results for the cut point will be considered confirmed in a direction that supports the proposition of enrichment provided the observed response rate in the confirmation set for subjects above the selected cut point is greater than or equal to the 20th percentile of its posterior predictive distribution as determined using the training set at the time the cut point is set. In other words, consistency of effect is defined as not belonging to the lower 20% of the training set's predictions for enrichment associated with use of the cut point.

Efficacy will be evaluated in the All Comer group and the PD-L1_H subgroup for Cohort A and B respectively. For the primary efficacy endpoint, the ORR based on RECIST 1.1 by the blinded central imaging vendor review, the point estimate, and 95% CI (as determined by the upper and lower 97.5% one-sided confidence bounds) will be provided using an exact binomial distribution. Subjects without response data will be counted as non-responders. Secondary efficacy evaluations of ORR based on RECIST 1.1 by investigator review, and

ORR based on modified RECIST 1.1 by blinded central imaging vendor review will also be conducted using the same methodology as for the primary efficacy analysis.

Duration of response by blinded central imaging vendor review and investigator review will be summarized using KM method in all responders.

For PFS and OS, KM curves, median estimates, and survival at 6, 12 and 18 months based on the KM curves (95% CI is based on Greenwood's formula) will be provided as appropriate. Subjects without efficacy evaluation data or without survival data will be censored at Day 1. The DCR will be summarized at the end of the trial. The restricted Mean Survival Time estimate of PFS and OS will also be calculated and plotted over time.

An outline of the key efficacy analysis strategy is presented in [Table 8](#).

Table 8 Analysis Strategy for Key Efficacy Endpoints

Endpoint	Statistical Method	Analysis Population	Missing Data Approach

 • ORR by BICR per RECIST1.1 • ORR by investigator assessment per RECIST1.1 	Exact test of binomial parameter; 95% CI [†]	FAS [‡] /ASaT	Subjects with missing data are considered non-responders

 • DOR by BICR per RECIST1.1 • DOR by investigator assessment per RECIST1.1 	Summary statistics using KM method	All responders	Non-responders are excluded in analysis

 • PFS by BICR and investigator assessment per RECIST 1.1 OS • Proportion of subjects with PFS at 6, 12 and 18 months; Proportion of survival at 6, 12, 18, and 24 months 	Summary statistics using KM method	FAS [‡] /ASaT	Censored at last assessment

 • DCR by BICR and investigator assessment per RECIST 1.1 	Exact test of binomial parameter; 95% CI [†]	FAS [‡] /ASaT	Subjects with missing data are considered non-responders
[†] 95% CI is determined by the upper and lower 97.5% one-sided confidence bounds. [‡] Primary population for efficacy analyses			

The strategy to address multiplicity issues with regard to multiple endpoints and interim analyses is described in Section 8.7 (Interim Analyses) and in Section 8.8 (Multiplicity).

The association between biomarker values and ORR will be investigated via logistic regression using one-sided tests on the regression coefficient. Cut-off evaluation and selection will involve a review of how the positive predictive value (PPV, response rate in those above a cut-off) and negative predictive value (NPV, response rate in those below the

cut-off) vary with putative cut-offs. A cut-off that maintains high NPV (e.g., above 90%) while achieving meaningful enrichment of response and largely capturing patients showing durable clinical benefit is ideal. The profiles of PPV, NPV, and the percentage of patients above a given cut-off along with intervals quantifying the uncertainty in those profiles will be estimated as a function of potential cut-offs. Receiver operating characteristic curve analysis will also be used to understand the sensitivity and specificity profile and examine cut-offs that might be suggested based on the ROC curve and their appropriateness with regard to PPV and NPV. If the operating characteristics associated with a single biomarker cutpoint are not sufficiently optimized, up to 2 biomarker cutpoints may be carried forward for efficacy endpoint analyses (i.e., a biomarker positive cutpoint and a biomarker high positive cutpoint), as has been implemented in other tumor types within the pembrolizumab program (e.g., bladder cancer) [44]. Details of the biomarker analysis strategy will be documented in the sSAP.

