Primary objective (2) is to evaluate ORR in subjects who fulfill the eligibility criteria for Cohort A and with higher expression of program cell death-ligand protein 1 (PD-L1) in tumor tissue samples. It is expected that higher PD-L1 expression in tumor tissue will be associated with better clinical responses to pembrolizumab (refer to Section 4 for background and rationale). In order to achieve this primary objective, a PD-L1 expression cutpoint will first be established with a goal to enrich the population for better clinical benefit. The cutpoint will be determined during the planned interim analysis using the clinical efficacy data and PD-L1 expression data from the first 100 enrolled Cohort A subjects. This data set is designated as the “training set” (refer to Section 8.7 on the approach for determining the PD-L1 cutpoint). In order to confirm the association of higher PD-L1 expression with increased clinical activity by pembrolizumab treatment, another 150 subjects who fulfill eligibility criteria for Cohort A will be enrolled, which is designated as the “confirmation set”. Cohort A will therefore, enroll a total of 250 subjects. Based on the established PD-L1 cutpoint from the training set, subjects in the confirmation set will be assigned into the subgroup with PD-L1 expression above or equal to the cutpoint (i.e., Cohort A PD-L1_H) or the subgroup with PD-L1 expression below the cutpoint (i.e., Cohort A PD-L1_L). Enrollment into Cohort A will not be interrupted for interim analysis. However, in order to ensure data integrity, samples from the “confirmation set” will not be assessed for PD-L1 expression until the cutpoint has been established and the assay has been confirmed. Based on the prevalence data regarding higher PD-L1 expression, the total enrollment of Cohort A may be increased to up to 280 to ensure a minimum of 60 subjects from the confirmation set (see below) will have PD-L1 expression above the expected cutpoint.

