3.3 Exploratory Objectives

- 1) To evaluate ORR, DOR, PFS as assessed by BICR per irRECIST 1.1.
- 2) To evaluate ORR, DOR, PFS as assessed by investigator per Gynecologic Cancer InterGroup (GCIg) criteria [2].
- 3) To characterize tumor microenvironment for immune-related features such as immune-related messenger RNA expression signatures, presence of tumor-infiltrating lymphocytes (TILs), PD-L1/ program cell death-ligand protein 2 (PD-L2) expression; and to characterize genetic changes/aberrations and mutational burdens within tumor tissues.
- 4) To assess correlations of the biomarkers and the clinical activity observed in the overall study population and various subgroups following pembrolizumab treatment.
- 5) Additional translational research may include T-cell clonality, neoantigen expression, presence and changes in circulating tumor markers such as circulating tumor DNA, serum microRNA and protein changes at screening and following pembrolizumab treatment, and evaluation of pharmacokinetics of pembrolizumab.
- 6) Variation across the human genome may be analyzed for association with clinical efficacy and/or safety data collected in this study.

For definitions of endpoints, refer to Section 8.4.1.

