8.8 Multiplicity

The primary objectives for ORR per RECIST 1.1 in All Comer Population and PD-L1_H subgroup for Cohort A and Cohort B will be assessed by point estimate and 95% CI. There are no formal hypotheses and no adjustments for multiplicity are planned. Evaluation of objectives should be interpreted with caution due to the potential for an increase in the false positive rate.

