The evaluation of a general positive association between CPS and BOR will be investigated via standard logistic regression as well as generalized additive models. The potential for a cut-off greater than CPS 1% to define a PD-L1 positive population with good clinical utility will depend on the strength of evidence in the observed association, as well as a detailed evaluation of the relative improvement in clinical utility with higher cut-offs. This evaluation involves a review of the positive predictive value (PPV, response rate in those above a cut-off), sensitivity (proportion

above the cutoff among responders), negative predictive value (NPV, non-response rate in those below the cut-off), specificity (proportion below the cutoff among non-responders), and fraction of PD-L1 positive patients (prevalence) as functions of increasing cut-offs. A clinically useful PD-L1 positive cut-off should maintain high NPV (e.g. near or above 90%) while achieving a meaningful enrichment of response, and largely capturing patients showing durable clinical benefit is sought. A receiver operating characteristic curve, and graphical illustrations will be utilized to assess the performance of a binary classifier and to understand the sensitivity and specificity profile in the context of PPV and NPV. Analyses will also be performed on PFS and OS, as appropriate, examining associations using cox proportional hazards models and KM estimates with graphical illustrations. CPS ranges for any promising cut-offs will also have to be gauged in the context of practical implementation and interpretation by pathologists in clinical practice.

The associations between clinical response and other biomarkers, e.g., immune-related mRNA expression signatures and somatic mutational load, will be evaluated similarly.

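### The rule that declares PD-L1 enrichment confirmed checks only that the PD-L1_H response rate is reproduced, so it can be met when PD-L1_H does no better than PD-L1_L in the confirmation set

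*Combined protocol and SAP*

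**What the plan says.** Protocol Section 2.1.1 splits Cohort A into a training set of 100 subjects, used to set the PD-L1 cut point, and a confirmation set of 150. It gives the purpose of the second set: "In order to confirm the association of higher PD-L1 expression with increased clinical activity by pembrolizumab treatment". Confirmation-set subjects are classed as PD-L1_H or PD-L1_L.

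Protocol Section 8.6.1 then gives the pass rule. It opens with the conclusion to be drawn: "Results for the cut point will be considered confirmed in a direction that supports the proposition of enrichment provided the observed response rate" clears a hurdle. The hurdle is set on the PD-L1_H group alone, and is cleared if the figure "for subjects above the selected cut point is greater than or equal to the 20th percentile of its posterior predictive distribution", that distribution being derived from training. The next sentence paraphrases this as consistency of effect.

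Below-cut data are used elsewhere:
- In choosing the cut, Section 8.6.1 reviews PPV, NPV and the ROC curve. It treats as ideal a cut that keeps NPV high (its example is above 90%) while "achieving meaningful enrichment of response and largely capturing patients showing durable clinical benefit is ideal".
- sSAP Section 3.6.1 says much the same: "A clinically useful PD-L1 positive cut-off should maintain high NPV (e.g. near or above 90%) while achieving a meaningful enrichment of response".
- Section 8.6.1 also plans a regression: "The association between biomarker values and ORR will be investigated via logistic regression using one-sided tests on the regression coefficient".
- Exploratory objective 4 (Section 3.3) is "To assess correlations of the biomarkers and the clinical activity observed in the overall study population and various subgroups following pembrolizumab treatment".

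Neither the regression nor the exploratory objective is a condition for calling the cut point confirmed. The sSAP does not repeat the rule, and its summary of changes does not withdraw it. The efficacy groups named in both documents are All Comer and PD-L1_H.

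**The concern.** Enrichment is a comparison: subjects above the cut respond more often than those below it. The rule looks at one side only. If PD-L1_H responds in the confirmation set about as training predicted, the rule is met whatever PD-L1_L does. A set enrolled to confirm an association could therefore yield a statement that enrichment was confirmed while its own data show no difference, or a difference in the wrong direction.

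At stake is that statement and any later use of the cut point that rests on it. The four primary ORR estimates and their exact intervals do not depend on the rule.

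**Working it through.** **Inputs from the plan.** Training n = 100; confirmation n = 150; PD-L1_H prevalence about 40%; expected ORR 25% in All Comers and above 35% in the enriched group (protocol Section 8.9).

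**Assumed, because the plan is silent.** Beta(0.5, 0.5) or Beta(1, 1) prior; 40% prevalence in training too (40 v 60); a cut fixed in advance; the numeric form of any training screen.

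**Plan's own figures.** 0.40 × 150 = 60 PD-L1_H subjects, leaving 90 PD-L1_L. The exact 95% CI for 15/60 is 14.7% to 37.9%, as in Table 10. The plan gives no operating characteristic for the 20th-percentile rule.

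**Step 1: the rule alone.** With x responders among 40 in training, the prediction for 60 new subjects is beta-binomial(60, a + x, a + 40 − x), where a = 0.5 or 1. The hurdle t(x) is its 20th percentile. The pass probability is

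Σₓ Bin(x; 40, p_H) × Pr[Bin(60, p_H) ≥ t(x)].

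The below-cut rate p_L does not appear. Over prevalences of 30–60% and both priors:
- no PD-L1 effect (25% in both groups): 80.7–82.8%
- 35% above the cut: 80.9–82.4%

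This near-equality is by construction, since a 20th-percentile predictive check passes about 80% of the time. At 40% prevalence with no effect, 36.7–37.1% of trials pass with an observed PD-L1_H rate no higher than PD-L1_L. That figure includes training results that the plan would probably not carry forward.

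**Step 2: adding a training screen.** The table gives the share of trials both carried forward and confirmed, at 40% prevalence. In the effect column the below-cut rate is (0.25 − 0.40 × 0.35)/0.60 = 18.3%. NPV is the non-response rate below the cut, as the sSAP defines it.

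| Assumed training screen | No effect (25% v 25%) | Effect (35% v 18.3%) |
|---|---|---|
| H − L above 0 | 32–33% | 78% |
| H − L at least 5 points | 18% | 72–73% |
| H − L at least 10 points | 6–7% | 60% |
| H > L and NPV at least 85% | 3.4% | not tabulated |
| H > L and NPV at least 90% | 0.25% | not tabulated |

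The NPV screen protects less when response is rare, because NPV is then high with or without a PD-L1 effect. At a common ORR of 12%, the 90% screen still leaves 21–22% of no-effect trials confirmed.

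**Step 3: what the rule permits.** After 12/40 v 13/60 in training, the hurdle is 14/60 under either prior. A confirmation result of 14/60 (23.3%) v 23/90 (25.6%) meets it, with a difference of −2.2 points (Newcombe 95% CI −15.5 to 12.2). This illustrates the confirmation rule only: the training NPV is 47/60 = 78.3%, short of the plan's target, so the plan might not have selected that cut.

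**Step 4: the missing contrast.** At 60 v 90 and 35% v 18.3%, a two-sided 95% CI for the difference lies above 0 in 62.5% of trials (Wald) or 64.2% (Newcombe). With no effect the figures are 2.4% and 2.7%.

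**The case against.** The strongest reply is that the design has two stages. Training looks for enrichment with below-cut data (NPV, ROC, one-sided regression). Confirmation then checks only that the PPV was not over-optimistic. This is fair, and three inferences that a reader might draw go too far:

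- *That PD-L1_L data are ignored throughout.* They are not; they are missing from the confirmation rule. The regression is not limited to training, so planned association analyses could use confirmation-set PD-L1_L data.
- *That the plan wrongly confirms enrichment about 81% of the time.* That is the rule in isolation. A demanding NPV screen brings the figure at 25% ORR below 1%.
- *That an NPV target near 90% contradicts the plan's own response rates.* Taking exactly 35% above the cut gives an NPV of 81.7%. But Section 8.9 says above 35%, and makes the 40% prevalence conditional. With 10% response below the cut, PD-L1_H would be (0.25 − 0.60 × 0.10)/0.40 = 47.5%, which is compatible.

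It is also true that the objectives are estimation only, that no alpha is attached, and that Section 8.8 warns: "Evaluation of objectives should be interpreted with caution due to the potential for an increase in the false positive rate".

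The central point survives. The NPV figure is an example, not a criterion, and meaningful enrichment has no number, so the protection cannot be stated in advance. A screen in training is not confirmation in the set enrolled for that purpose. The caution in Section 8.8 does not supply the missing comparator. Nor does All Comer ORR, which mixes both PD-L1 groups and includes training subjects.

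**Conclusion.** The point stands on the text and should be fixed. The rule measures reproducibility of the PD-L1_H rate but is worded as confirmation of enrichment, and it can be met with no difference between the groups.

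How often that would happen cannot be fixed from the documents. With no true effect at 25% ORR it runs from about a third of trials to well under 1%, depending on a training screen that the plan leaves open. These figures assume the prior, the screen, a fixed cut and 40% prevalence in training. The reading of the rule needs none of them.

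The consequence is limited to the enrichment statement. The documents do not support inferring any fault in the ORR estimates or intervals.

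**What to change.** In protocol Section 8.6.1, cross-referenced in sSAP Section 3.6.1:

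1. Describe the 20th-percentile check as consistency (reproducibility) of the PD-L1_H response rate, and remove the enrichment wording from it.
2. In the confirmation set, for each cut point carried forward, report PD-L1_L ORR with its exact 95% CI and the PD-L1_H minus PD-L1_L difference with a 95% CI. Base any statement that enrichment was confirmed on that difference.

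This stays within an estimation plan. Whether to set a numeric bound, and which, is the sponsor's choice. For scale, at 60 v 90 a one-sided 90% lower bound above 0 is met in 9.6% of trials with no effect and 83.8% with 35% v 18.3%.

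The cost is wording in two documents and one extra table, from subjects already enrolled, scanned and scored. The real price is that the enrichment statement becomes harder to reach: in the effect scenario, a 95% CI wholly above 0 is expected in only about 62–64% of trials.

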3.0 OBJECTIVE(S) & HYPOTHESIS(ES)

3.1 Primary Objective(s) & Hypothesis(es)

In subjects with advanced ROC:

- 1) **Objective:** To evaluate clinical anti-tumor activity of pembrolizumab monotherapy based on ORR as assessed by BICR per RECIST 1.1 in Cohort A-All Comer group as defined in Section 2.1
- 2) **Objective:** To evaluate clinical anti-tumor activity of pembrolizumab monotherapy based on ORR as assessed by BICR per RECIST 1.1 in Cohort A-PD-L1_H subgroup, as defined in Section 2.1, using a PD-L1 expression cutpoint established in the training set.
- 3) **Objective:** To evaluate clinical anti-tumor activity of pembrolizumab monotherapy based on ORR as assessed by BICR per RECIST 1.1 in Cohort B-All Comer group as defined in Section 2.1
- 4) **Objective:** To evaluate clinical anti-tumor activity of pembrolizumab monotherapy based on ORR as assessed by BICR per RECIST 1.1 in Cohort B PD-L1_H subgroup, as defined in Section 2.1, using a PD-L1 expression cutpoint established in the training set from Cohort A

The primary objectives will focus on estimation of ORR, and no formal hypothesis testing is planned. If the operating characteristics associated with a single biomarker cutpoint are not sufficiently optimized, up to 2 biomarker cutpoints may be carried forward for efficacy endpoint analyses (see Section 8.6.1).

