8.0 STATISTICAL ANALYSIS PLAN

This section outlines the statistical analysis strategy and procedures for the study. If, after the study has begun, but prior to any unblinding/final database lock, changes made to primary and/or key secondary hypotheses, or the statistical methods related to those hypotheses, then the protocol will be amended (consistent with ICH Guideline E-9). Changes to exploratory or other non-confirmatory analyses made after the protocol has been finalized, but prior to final database lock, will be documented in the supplemental Statistical Analysis Plan SAP (sSAP) and referenced in the Clinical Study Report (CSR) for the study. Post-hoc exploratory analyses will be clearly identified in the CSR. The sSAP will also document the detailed biomarker analysis strategy including determination of the PD-L1_H cut-off selection.

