8.9 Sample Size and Power Calculations

Based on the preliminary data of pembrolizumab in ovarian cancer patients as described in Section 4.1.2, we expect an ORR of approximately 25% for the All Comer population. These responding subjects expect to have durable responses. In addition we expect additional subjects will have durable SD. We expect in a PD-L1 enriched population, ORR may reach to above 35% with durable response in majority of the subjects.

Table 9 shows the two-sided 95% CI of ORR for different observed response rates based on different sample size in the All Comer group for Cohort A or Cohort B.

Table 9 Two-sided 95% Confidence Interval of ORR in All Comer

Sample Size	Observed ORR	95% CI of ORR (%)
75	17%	(9.3, 27.4)
	25%	(15.7, 36.3)
	30%	(20.0, 41.7)
	35%	(24.3, 46.9)
100	17%	(10.2, 25.8)
	25%	(16.9, 34.7)
	30%	(21.2, 40.0)
	35%	(25.7, 45.2)
180	17%	(12.0, 23.5)
	25%	(18.9, 32.0)
	30%	(23.4, 37.3)
	35%	(28.1, 42.4)
250	17%	(12.7, 22.5)
	25%	(20.0, 31.1)
	30%	(24.4, 36.1)
	35%	(29.3, 41.5)

For the PD-L1_H subgroup, if the prevalence of PD-L1_H is about 40%, there will be approximately 60 PD-L1_H subjects if there are 150 all comer subjects in the confirmation set, and approximately 30 PD-L1_H subjects if there are 75 all comer subjects in Cohort B. Table 10 shows the two-sided 95% CI of ORR with 30 and 60 subjects for different response rates.

Table 10 Two-sided 95% Confidence Interval for ORR in PD-L1_H

Sample Size	Observed ORR	95% CI of ORR (%)
30	25%	(12.2, 45.9)
	30%	(14.7, 49.4)
	35%	(17.3, 52.8)
	40%	(22.7, 59.4)
60	25%	(14.7, 37.9)
	30%	(18.9, 43.2)
	35%	(23.1, 48.4)
	40%	(27.6, 53.5)

The sample size for the training set (n=100), was selected to achieve adequate precision on the PPV and NPV profiles as a function of putative cut-offs.

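### Does the protocol's definition of NPV as a response rate below the PD-L1 cut-off put the choice of cut-off at risk?

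*Combined protocol and SAP*

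**What the plan says.** Protocol Section 8.6.1 describes how candidate PD-L1 cut-offs will be compared in the training set. It defines PPV as the response rate above a cut-off and, in the same sentence, "negative predictive value (NPV, response rate in those below the" cut-off. The next sentence says that a cut-off that "maintains high NPV (e.g., above 90%) while achieving meaningful enrichment of response and largely capturing patients showing durable clinical benefit is ideal".

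Section 3.6.1 of the supplemental SAP (sSAP) covers the same ground and words the measure as "negative predictive value (NPV, non-response rate in those below the cut-off". It also defines sensitivity and specificity, and it asks for an NPV near or above 90%.

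Two places in the protocol say which document holds the detail. Section 8.0 states: "The sSAP will also document the detailed biomarker analysis strategy including determination of the PD-L1_H cut-off selection". Section 8.6.1 closes the topic with: "Details of the biomarker analysis strategy will be documented in the sSAP".

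The planning values are in protocol Section 8.9: "we expect an ORR of approximately 25% for the All Comer population", an ORR that may exceed 35% in a PD-L1 enriched population, and subgroup sizes worked out "if the prevalence of PD-L1_H is about 40" percent.

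**The concern.** The two documents attach the same label to opposite quantities: if one reports p, the other reports 1 − p. The protocol also disagrees with itself, because a response rate above 90% below the cut-off does not fit with enrichment above it at any response rate the plan expects.

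The measure is not incidental. It is one of the stated criteria for choosing the cut-off, and the cut-off defines the PD-L1_H groups for primary objectives 2 and 4. The training set of 100 is justified by the precision of the PPV and NPV profiles. If an analyst applied the protocol sentence as written, the search would favour cut-offs that leave responders in the PD-L1-low group. That would be a serious error in a rule on which two of the four primary objectives depend.

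**Working it through.** **Planning inputs (protocol Section 8.9).** Overall ORR 25%, PD-L1_H ORR 35% (worded as a value that may be exceeded), PD-L1_H prevalence 40% (worded as a conditional). The section's own subgroup counts reproduce: 150 × 0.40 = 60 in the confirmation set and 75 × 0.40 = 30 in Cohort B. The 90% is given as an example and is not derived, so there is no stated NPV to reproduce.

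**Identity used.** With prevalence *v*, response rate above the cut-off *a* and response rate below it *b*:

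ORR = *v* × *a* + (1 − *v*) × *b*

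**Literal protocol reading (NPV = *b*).**

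- Largest possible *b* at ORR 25% and *v* = 40%, taking *a* = 0: 0.25 / 0.60 = 41.7%. This is far short of 90%.
- Overall ORR needed for *b* = 90% at *v* = 40%, even with no responders above the cut-off: 0.60 × 0.90 = 54%, against an expected 25%.
- Prevalence needed for *b* = 90% at ORR 25%: at least 1 − 0.25/0.90 = 72.2%. At 80% prevalence, *a* = (0.25 − 0.90 × 0.20) / 0.80 = 8.75%. The group above the cut-off would then respond less often than the whole cohort, which is the opposite of enrichment.

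In general, ORR is a weighted average of *a* and *b*. If *b* exceeds 90% and ORR is below 90%, *a* must be below ORR. The contradiction therefore depends on overall ORR being under 90%. It is not a pure matter of logic: 91% below and 99% above would satisfy both statements. No planning figure comes near that range.

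**sSAP reading (NPV = 1 − *b*).** At 25%, 35% and 40%:

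- *b* = (0.25 − 0.40 × 0.35) / 0.60 = 0.11 / 0.60 = 18.3%
- NPV = 1 − 0.183 = 81.7%

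This is on the scale of the 90% example, and it would be higher if PD-L1_H ORR exceeded 35% at the same ORR and prevalence.

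**Where the measure is used.** NPV enters only the choice of cut-off at the interim analysis. The confirmation rule in protocol Section 8.6.1 compares the observed response rate above the cut-off with the 20th percentile of its predictive distribution, and the primary estimates are exact binomial intervals for ORR. Neither uses NPV. Within the cut-off search, *b* and 1 − *b* come from the same counts, so a profile of one is the mirror image of the other.

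**The case for a change.** The strongest argument for amending is that the sSAP calls itself a companion to the protocol SAP, so the wrong wording sits in the principal document. The sSAP's summary of changes does not record a corrected definition. Protocol Section 10.7 says that both documents go to journals with a manuscript, so an outside reader would see two opposite definitions. On the planning values these would give 18.3% and 81.7% from the same data. The correction would be one prefix.

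The textual point stands: the protocol sentence is wrong as written, and adding the prefix would do no harm if the section were opened for another reason. The consequence does not follow. The protocol itself hands the cut-off strategy to the sSAP, and the sSAP definition is correct. Even a reader with the protocol alone has the name of the measure, its pairing with PPV and the 90% example, which together leave one workable meaning.

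Nor does the distance between 81.7% and 90% show a second fault. The 35% is worded as a value that may be exceeded, the 40% illustrates subgroup size and does not forecast the chosen cut-off, the 90% is an example, and protocol Section 3.1 allows that "up to 2 biomarker cutpoints may be carried forward for efficacy endpoint analyses".

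A wording change would also probably come too late to matter. The current protocol is dated January 2020, the original November 2015, and the cut-off is set once the first 100 Cohort A subjects have at least 4 months of follow-up. That the selection was already complete is an inference; the documents do not say so.

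**Conclusion.** This is a clerical slip, and no change to the plan follows. The protocol's NPV definition lacks a 'non-'; the sSAP, to which the protocol assigns the cut-off strategy, has it right. The effect on ORR estimates, confidence intervals, sample size and selection of the cut-off is nil. That rests on two things: analysts follow the protocol's referral to the sSAP, and overall ORR is far below 90%, so that the literal wording cannot be put into practice. The expected ORR of about 25% meets the second condition with a wide margin.
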